## Variables

**Primary outcome variables** (Form to be filled at untreated baseline and every change in treatment status: From untreated to treated or vice versa, from one treatment to another.

### *Registration of treatment*

All patients included in the trial are considered treatment naïve at inclusion in the observational period (01.01.2001). Registration of initiation, change or cessation of treatment will follow the following structure:

Date (Date)	Drug (Name)	Action* (Categorical)	Dose (Integer)	Dose interval (Comment)	Comment (Comment)
----------------	----------------	--------------------------	-------------------	----------------------------	----------------------

\*Action is restricted to four levels: initiation, increase, decrease, cessation.

Cardiac events		
Date of event	Cardiac event	Yes/No
	Myocardial infarction	Yes No
	Unstable angina pectoris	Yes

		No
	PCI / CABG	Yes No
	Heart Failure	Yes No
	Arrhythmia (New onset of symptomatic arrhythmia requiring anti-arrhythmic Medication)	Yes No
	Heart procedure (pacemaker/ICD/valve surgery)	Yes No

Renal events		
Date of event	Renal event	Yes/No
	Doubling of s-creatinine	Yes No
	ESKD	Yes No

Cerebrovascular events		
Date of event	Cerebrovascular event	Yes/No
	Stroke	Yes No
	TIA	Yes No

#### **Variables of interest at inclusion**

Variables of interest at inclusion consists primarily of time invariant variables.

#### Demographics

Date of Birth	• DDMMYYYY
Sex	• Male • Female
Ethnicity	White Black Asian

	Others
City	Residence City

Fabry-specific disease background

Age of first symptoms	Years
Age of diagnosis	Years
Fabry family history	Yes No Unknown
Index case	Yes No
ALPHA GAL ACTIVITY (LEUCO ASSAY) at inclusion	% of normal activity
MOLECULAR TEST	Amenable mutation found: Other mutations

## Exploratory outcome variables

*Variables concerning clinical presentation*

ANGIOKERATOMA	Yes No
CORNEA VERTICILLATA	Yes No
ABDOMINAL PAIN	Yes No
REFLUX	Yes No
INDIGESTION	Yes No
DIARRHEA	Yes No
CONSTIPATION	Yes No
DYSPNOEA	Yes No

NEUROPATHIC PAIN	
 
• Yes
 
• No
 

ACROPARAESTHESIA	
 
• Yes
 
• No
 

DEPRESSION SYMPTOMS	
 
• Yes
 
• No
 

*Variables concerning organ dysfunction*

Lung capacity	
Clinically significant Changes in spirometry of obstructive function	Yes No
Clinically significant changes in spirometry of restrictive function	Yes No
Neurological / Audiological	
Pathological heart rate variability	Yes No

Impaired hearing audiogram	Yes No
Vertigo	Yes No

BLOOD PRESSURE	mmHg
Heart Rate	BPM

BUN	mmol/l
Plasma CREATININE	mmol/l
URINARY CREATININE	mg/dl
ALBUMIN/CREATININE RATIO	mg/g
PROTEINURIA	mg
GFR CKD-EPI	ml/min/1,73m 
mGFR	ml/min
Plasma Gb3	microgram/ml
Plasma lysoGb3	ng/ml
Urine GB3	microgram/mmol creatinine
Alpha GAL-A activity (DBS or Leuco assay)	% normal activity and quantitative concentration (Method reference)

#### Variables concerning concomitant medication

The included concomitant medication to be recorded is restricted to medications believed to be of clinical interest. Medication will be recorded as to their use at inclusion and regarding their change throughout the study if possible.

Concomitant medication at inclusion	
ACE-I/ ARB	Yes No
Beta-blocker	Yes No
Ca-blockers	Yes No

Diuretics	Yes No
Statins	Yes No

Date (Date)	Drug (Name)	Action* (Categorical)	Dose (Integer)	Dose interval (Comment)	Comment (Comment)
----------------	----------------	--------------------------	-------------------	----------------------------	----------------------

\*Action is restricted to four levels: Initiation, decrease, increase, cessation.

## Other variables and exploratory outcome variables

### Safety variables

#### Safety Endpoints

Although the study collects retrospective secondary data, adverse event reporting will be conducted, if necessary, in line with the requirements of each study supporter.

- SAEs
- Vital signs:
  - resting systolic blood pressure
    - resting diastolic blood pressure
  - Body weight
- Overall survival among all patients enrolled, as assessed by recorded patient deaths from any cause
- Laboratory parameters:
  - serum creatinine
    - urine creatinine
    - urine protein
    - urine albumin
    - urine ACR
- ECGs
- ECHOs, including left ventricular mass index (LVMi), if medically indicated and requested by a physician
- Occurrence of male infertility.
- Infusion related reactions and other key safety events

## ***Data sources***

### **Data sources for primary endpoints**

Electronic medical records, paper records and national medical records

### **Other data sources**

Not applicable

## ***Study size***

The study is estimated to comprise of approximately 115 individuals with genetically verified Fabry Disease (Ratio of sex [female:male] 2:1).

## ***Data management***

### **Data collection**

Investigators or other designated site staff are implemented in the project group will be trained in the specific procedural steps of the protocol, data extraction.

Study variables will be recorded in an electronic database/ CRF using validated and secure database in RedCap©. Patient data will be handled while preserving confidentiality. Investigators, or other designated site staff, will analyze all Fabry patients irrespective of disease-causing mutation and will extract clinical and laboratory parameters from original medical records (primary data sources).

## ***Validation procedures***

A 10% random sample of records will be reviewed by a second independent observer to assure quality. The investigator team will discuss and resolve any noted discrepancies.

## ***Case report form***

All CRFs will be completed by the Investigators or other designated site staff who have been trained to record relevant information.

Data will be acquired retrospectively from medical documentation of enrolled patients.

Study variables will be recorded in a CRF designed for the specific purpose of this study. CRF design will be reviewed. At the end of data acquisition, the extent of missing values will be evaluated, and handled according to the description in the statistical analysis plan.

All patient data will be handled while preserving confidentiality.

## **Data management**

All CRFs will be completed by the Investigators or other designated site staff who have been trained to record relevant information. Designated staff responsible for data acquisition should have higher medical education.

Data will be captured retrospectively from medical record documentation.

Study variables will be recorded in an electronic CRF by RedCap. CRFs will be reviewed for completeness at the end of document completion for data check (of missing data and/or specific questions requiring the investigators patient knowledge). All patient data will be handled preserving confidentiality.

## **Medical coding**

Not applicable.

## **Serious Adverse Events/Adverse Events Data Reconciliation**

Although the study collects retrospective secondary data, reporting of adverse events will be conducted, if necessary, in line with the requirements of each study supporter. In the event of not previously reported serious adverse events or suspected, unexpected serious adverse reactions to a subscriber's product, these events will be reported to Competent Authorities within 24 hours.

## **Database lock**

At the completion of data acquisition, all interested parties will be informed of impending data lock. Data lock will transpire if all parties agree, but before the independent validation by an external party and before statistical analysis.

## ***Data analysis***

### **Descriptive statistics**

Analyses will be performed by descriptive statistical methods. Continuous variables will be described with number of patients with valid/missing observations, mean, standard deviation, median, minimum and maximum. Non-normally distributed data will be presented as median and interquartile range as appropriate. Categorical variables will be described by frequencies and related percentages. In addition to descriptive analysis, many of the endpoints will undergo statistical testing (i.e., p-values, confidence limits) to provide inferential summaries of subgroup comparisons (such as gender, age, ethnicity).

Details are going to be described in the Statistical Analysis Plan (SAP).

Analysis will be stratified by sex, age (> or <40 years), Fabry specific therapy (ERT treated (agalsidase alfa and beta separately), Migalastat treated, treatment naïve), baseline organ involvement (cardiac, renal, cerebrovascular, peripheral nervous system, and gastrointestinal system). Additional analysis may be required and carried out based on the results of the analyses mentioned above.

## **Handling of missing data**

Missing data will not be imputed.

## **Primary endpoints analysis**

Kaplan-Meier plots will be used to assess time to first Fabry associated clinical event (FACEs). Cox proportional hazard models will be used to assess the association between baseline characteristics and incident Fabry associated clinical event. The following baseline variables will be used in the model as covariates: age, time since diagnosis of Fabry disease, previous FACE (renal, cardiac, or cerebrovascular).

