## **Endpoints**

### **Primary endpoints**

The primary endpoint is time to first FACE (cardiac, renal, or cerebrovascular events) since each baseline, with particular focus on the added value of the recent addition of Migalastat as a treatment option.

FACEs are defined as the following:

- Cardiac clinical events:
  - Myocardial infarction
  - New symptomatic arrhythmia requiring medication, direct current cardioversion, or interventional procedure (e.g., ablation, pacemaker, or defibrillator implantation)
  - Unstable angina defined by national practice guidelines and accompanied by electrocardiographic changes and non-ST segment elevation myocardial infarction [UA/NSTEMI]) and accompanied by electrocardiographic changes
  - Congestive heart failure requiring hospitalization
  - Any major cardiac medical procedure (e.g., valve replacement, stent-implantation, transplant or persistent atrial fibrillation)
- Cerebrovascular clinical events
  - Stroke (documented by a physician)
  - Transient ischemic attack (documented by a physician)
- Renal clinical events
  - Doubling of serum creatinine level from the start of analysis (2 consecutive values)
  - End-stage renal disease (ESRD) requiring long-term dialysis or transplantation
- Death due to FACEs

All FACEs will be analyzed together as a composite endpoint and separately in each category (cardiac, cerebrovascular, and renal).

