3. STUDY ENDPOINTS

3.1. Primary Effectiveness Analysis

The primary endpoint is time to first FACE (cardiac, renal, or cerebrovascular events) ") since start of treatment for migalastat and or ERT and from time of diagnosis for untreated with particular focus on the added value of the recent addition of migalastat as a treatment option. A formal statistical analysis will be using the initial treatment cohort. Descriptive statistics will be calculated since each start of treatment (after each switch).

FACEs are defined as the following:

- Cardiac clinical events:
 - Myocardial infarction
 - New symptomatic arrhythmia requiring medication, direct current cardioversion, or interventional procedure (e.g., ablation, pacemaker, or defibrillator implantation)
 - Unstable angina defined by national practice guidelines and accompanied by electrocardiographic changes and non-ST segment elevation myocardial infarction [UA/NSTEMI]) and accompanied by electrocardiographic changes
 - Congestive heart failure requiring hospitalization
 - Any major cardiac medical procedure (e.g., valve replacement, stent-implantation, transplant, or persistent atrial fibrillation)
- Cerebrovascular clinical events:
 - Stroke (documented by a physician)
 - Transient ischemic attack (documented by a physician)
- Renal clinical events
 - Doubling of serum creatinine level from the start of analysis (2 consecutive values)
 - End-stage renal disease (ESRD) requiring long-term dialysis or transplantation
- Death due to FACEs

All FACEs will be analyzed together as a composite and separately in each category (cardiac, cerebrovascular, and renal). Death due to FACE will be analyzed under the category in which it occurred (cardiac, cerebrovascular, or renal).

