6.2. Missing Assessments

All data will be listed as collected. Descriptive statistics will be calculated on the data collected without replacement. For time to event, analysis data will be censored.

Missing and partial dates will be replaced as described in Section [6.1](#).

While it is possible that some patients will have missing or partial date information for SAEs or other safety data collections, analyses of the safety endpoints will include all patients in the Safety Population, unless specifically stated otherwise.

Missing data might be present for the analyses of the clinical laboratories and vital signs (eg, where the parameter was not measured at a required time points, which are the dates of treatment switch), and PROs. In many situations, there will often be other measurements of the parameter within a time frame that is applicable eg. during each treatment period. In such cases, the closest measurement to the switch time point within the treatment period will be used for analysis (Section 11). If such a measurement does not exist, then the patient will be excluded from the analysis of that variable at that timepoint. If 2 measurements are equidistant from the scheduled time point, the first one will be used.

Estimated GFR and LVMi data will be used as is and the actual time of the measurement will be utilized in the analysis. Analysis of LVMi will be exploratory.

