13.1.1. Cox Proportional Analysis for Fabry-associated Clinical Events

The time to the first event is defined as time from the Analysis Start Date to the first composite FACE (primary interest), and to the first cardiac, cerebrovascular, renal clinical event, or death due to FACEs. For the primary analysis, patients who complete the study without an event, are lost to follow-up, discontinued the study, started dialysis, had a kidney or heart transplant, or after 30 days they changed/switched therapy (migalastat group) or after they start therapy (untreated group) will be censored. Describing effectiveness in migalastat treated population is of the main interest.

Treatment Switch

The primary analysis will address events that occur on therapy from the Analysis Start Date up until 30 days after the patient stops therapy or switches therapy. The events that happen afterwards will be excluded. For the patients untreated at time of diagnosis, the primary analysis will address events from the time of diagnosis until the patient starts a therapy. The events that happen afterwards will be excluded. An additional analysis will be performed:

1. An analysis that will address events that occur on therapy from the time of Analysis Start Date up until the patient stops therapy or patient switches therapy. For the untreated patients, the analysis will address assessments from the time of diagnosis until the patient starts a therapy. The events that happen afterwards will be excluded.

Primary Analysis Method

The ratio of the hazards of treatment groups will be checked to ensure that the hazard ratios are constant over time. Secondly, the assumption that each variable in the model makes a linear contribution will be checked.

The covariates will include:

- sex
- age at the Analysis Start Date as a continuous variable
- eGFR_{CKD-EPI} at the Analysis Start Date as a continuous variable
- LVMi at the Analysis Start Date
- previous history of cardiac, cerebrovascular, and renal clinical events (composite event) as related to Analysis Start Date
- Length of treatment for Fabry disease

If the measurements are not available, measurements prior to and closest to the Analysis Start Date will be used. In case that more than 50% of values are missing for a given covariate, it will be dropped from the analysis.

The estimate of hazard ratio for migalastat-treated/untreated along with the associated 95% CI will be calculated.

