A sensitivity analyses will be done using Kaplan-Meier approach (log-rank test).

The analysis between migalastat and ERT will be performed like the analysis above for the comparison between migalastat treated and untreated patients. The origination of analysis will be start of treatment.

Because patients could switch treatment many times during the 20-year period, the time to the first event within each treatment period will be calculated from each switch date and descriptive statistics will be presented. Please note that each patient could be counted more than once in this analysis. Two options will be used for these analyses. The first analysis will address events that occur on therapy from the Analysis Start Date up until 30 days after the patient stops therapy or from the switch date to the date of a subsequent switch or stopping therapy. The second analysis will address events that occur on therapy from the Analysis Start Date up until the patient stops therapy or switches therapy or from the switch date to the date of a subsequent switch or stopping therapy.

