13.4. Secondary Endpoint: Time to first FACE by Category

Time to the first cardiac, cerebrovascular, and renal clinical event separately by each specific category (including death in these categories) from start of treatment or time of diagnosis will be analysed in the same way as the primary endpoint - composite FACEs (section 13.1).

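### No rule is given for deaths that are not events in the endpoint; censored by default, they make the long category-specific Kaplan-Meier curves overstate absolute risk.

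*Protocol*

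**What the plan says.** The protocol, under Primary endpoints analysis, plans that "Kaplan-Meier plots will be used to assess time to first Fabry associated clinical event (FACEs", with Cox models for associations. Under Primary endpoints it adds: "All FACEs will be analyzed together as a composite endpoint and separately in each category (cardiac, cerebrovascular, and renal".

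The SAP makes a Cox model the primary method and gives Kaplan-Meier a supporting role: "A sensitivity analyses will be done using Kaplan-Meier approach (log-rank test" (13.1.1). For time to first event by category, 13.4 says the endpoint "will be analysed in the same way as the primary endpoint".

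On deaths, SAP 3.1 says: "Death due to FACE will be analyzed under the category in which it occurred (cardiac, cerebrovascular, or renal". The censoring rule in SAP 13.1.1 begins with "patients who complete the study without an event, are lost to follow-up, discontinued the study, started dialysis, had a kidney or heart transplant" and goes on to therapy change or therapy start. Death outside the endpoint is not on the list. The only general rule is in SAP 6.2: "For time to event, analysis data will be censored". Neither document mentions competing events or a cumulative incidence function.

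**The concern.** A patient who dies of stroke can no longer have a first cardiac or renal FACE. A patient who dies of a non-FACE cause can no longer have any FACE. In Kaplan-Meier each patient either has the event or is censored, so without another rule these deaths become censored times. The curve then treats the dead as if they could still have the event later, and one minus the curve estimates risk in a setting where nobody dies of anything else.

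Such deaths should be expected. The protocol's ethics section provides for enrolling deceased patients, and SAP 3.2.2 records deaths from any cause. Time to a first event by category is a stated secondary objective, and plots of this kind are commonly read as the risk that patients face. The overstatement grows with follow-up and with the rate of competing death, so groups that differ in either would be distorted unequally on one plot.

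**Working it through.** The plan states no event rate, death rate, power or cumulative risk, so it has no figure to reproduce. The check compares the two estimators over a range of assumed rates.

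**Inputs from the documents**
- About 115 patients (protocol, Study size).
- Longest follow-up: from 1 January 2001 to the end of 2022 is 22.0 years (protocol). To the end of 2023, the SAP's end date, it is 23.0 years (SAP 2).
- Migalastat available from 2016 (protocol, Rationale and background), so at most about 7.0 to 8.0 years on treatment.

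**Assumptions**
- Constant category event hazard *a* of 1%, 2% or 3% per year.
- Constant competing death hazard *c* of 0.5% to 3% per year.

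**Formulas**
- One minus Kaplan-Meier, competing deaths censored: 1 − exp(−*a t*).
- Cumulative incidence, which Aalen-Johansen estimates: *a*/(*a*+*c*) × [1 − exp(−(*a*+*c*) *t*)].

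**Worked example**, *a* = *c* = 0.02
- At 20 years: 1 − exp(−0.40) = 33.0%, against 0.5 × [1 − exp(−0.80)] = 27.5%. The excess is 5.4 points before rounding.
- At 7 years: 1 − exp(−0.14) = 13.1%, against 0.5 × [1 − exp(−0.28)] = 12.2%. The excess is 0.9 points.

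**Results at 20 years**

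| Event rate/yr | Competing death/yr | 1 − KM | Cumulative incidence | Excess (points) |
|---|---|---|---|---|
| 1% | 0.5% | 18.1% | 17.3% | 0.8 |
| 1% | 1% | 18.1% | 16.5% | 1.6 |
| 2% | 0.5% | 33.0% | 31.5% | 1.5 |
| 2% | 1% | 33.0% | 30.1% | 2.9 |
| 2% | 3% | 33.0% | 25.3% | 7.7 |
| 3% | 3% | 45.1% | 34.9% | 10.2 |

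Over the whole grid the excess is 0.8 to 10.2 points at 20 years (ratio 1.05 to 1.32) and 0.1 to 1.8 points at 7 years (ratio 1.02 to 1.11). With no competing death it is zero.

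**Against sampling error.** In 2,000 simulated cohorts of 115 with *a* = 2%, the standard deviation of the Kaplan-Meier estimate at 20 years was as follows.
- *c* = 1%: 4.6 points with full follow-up and 8.3 with entry spread over 22 years. The excess is 2.9/4.6 = 0.63 and 2.9/8.3 = 0.35 of it.
- *c* = 2%: 4.9 and 8.9 points. The excess is 5.4/4.9 = 1.10 and 5.4/8.9 = 0.61 of it.

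Spread entry is closer to this cohort, because patients enter at diagnosis and were found by cascade screening over two decades. Censoring at therapy change was not simulated and would widen the sampling error further.

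**Composite.** Here FACE deaths are events and only non-FACE deaths compete. As an illustration, 3% events and 0.5% competing death give 45.1% against 43.1% at 20 years, an excess of 2.0 points.

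**The case against.** The strongest case against is that the affected quantity is not a planned estimate. The SAP's primary result is a Cox hazard ratio, and Kaplan-Meier serves as plots and a log-rank sensitivity analysis. Censoring competing deaths leaves the Cox model as a valid model of the cause-specific hazard and the log-rank test as a valid test of it. Incidence is planned per 1000 person-years (protocol, Secondary endpoints analysis; SAP 13.3), where a death simply ends the person-time. All of this stands, and it confines the point to curves read as absolute risk.

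A reader might infer three stronger things that the documents do not support.
- *That the SAP orders these deaths to be censored.* It does not. The list in 13.1.1 omits death, and 8.2 lists reason for discontinuation and primary cause of death as separate items, so death cannot be assumed to fall under discontinuation. The censoring follows from the method's default where a rule is missing.
- *That the 20-year overstatement applies to the migalastat comparison.* On-treatment migalastat curves span at most about 7 to 8 years, where the excess was under 2 points on the assumed grid. One qualification: SAP 3.1 starts the clock at treatment for treated patients, while 11.2 starts it at diagnosis for migalastat against untreated. Under the second definition the curve could run longer.
- *That the primary composite is equally affected.* Only non-FACE deaths compete there, so the set of competing deaths is smaller.

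It is also fair to say that the bias is mostly smaller than one standard error once entry is spread over time. It is nonetheless systematic, always in one direction, and avoidable.

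**Conclusion.** The concern holds in limited form. The plan uses Kaplan-Meier for the composite and for each category, counts a FACE death only in its own category, and gives no rule for other deaths. Followed with the method's default, the category curves overstate absolute risk, chiefly those from diagnosis in long-untreated patients or the whole cohort.

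The direction is certain: with competing deaths censored, one minus Kaplan-Meier is never below the cumulative incidence. The size is unknown. The range of about 1 to 10 points at 20 years, and under 2 points at 7 years, rests entirely on assumed constant rates of 1-3% per year for events and 0.5-3% for competing death. The treatment hazard ratio, the log-rank test and the incidence rates do not need to change on this account.

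**What to change.** In SAP 13.1.1 and 13.4, and in the protocol's Primary endpoints analysis:
- State that a death not counted in the endpoint is a competing event: non-FACE death for the composite, and also death in another FACE category for each category analysis.
- Show Aalen-Johansen cumulative incidence curves in place of one minus Kaplan-Meier. This is essential for the categories and minor for the composite.
- Keep the cause-specific Cox model and the log-rank test for group comparisons. Gray's test is optional.
- Tabulate competing deaths by treatment group and endpoint.

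SAP 13.1.1 also censors at dialysis and at kidney or heart transplant. The same paragraph should say how these are treated in curves for categories where they are not themselves events; otherwise those curves will still not be plain absolute risks.

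The cost is some SAP wording, slightly more analysis work with standard procedures, and slightly lower displayed risks. No new data appear to be needed, since SAP 8.2 already lists primary cause of death and SAP 13.1 has FACEs adjudicated.

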11.2. Definition of the Migalastat or ERT Treatment Start or Treatment Switch

For analysis, if assessments were not collected on the treatment start date or a treatment switch date, then the assessment closest to the treatment start date will be utilized. If there are 2 assessments that are equidistant from the treatment start date, then the assessment prior to treatment start date will be utilized. Only assessments performed on that treatment will be used.

Treatment start date is used as the Analysis Start Date for comparing migalastat and ERT-treated patients. Diagnosis date is used as the Analysis Start Date for comparing migalastat and untreated patients.

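### The SAP drops time since diagnosis from the protocol's Cox covariates without declaring it, which leaves the additional migalastat-versus-ERT hazard ratio unadjusted for it

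*Protocol*

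**What the plan says.** The protocol's section on the primary endpoints analysis contains its only Cox specification. It says "Cox proportional hazard models will be used to assess the association between baseline characteristics and incident Fabry associated clinical event" and gives the covariates as "age, time since diagnosis of Fabry disease, previous FACE (renal, cardiac, or cerebrovascular".

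SAP 13.1.1 sets out a longer list: sex, "age at the Analysis Start Date as a continuous variable", eGFR, LVMi, "previous history of cardiac, cerebrovascular, and renal clinical events (composite event) as related to Analysis Start Date" and "Length of treatment for Fabry disease". Time since diagnosis is not there. It is also missing from the covariate lists in SAP 13.7 (eGFR) and 15.4 (overall survival).

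The same section then extends the model to a second comparison: "The analysis between migalastat and ERT will be performed like the analysis above for the comparison between migalastat treated and untreated patients". For that comparison it adds "The origination of analysis will be start of treatment", and SAP 11.2 agrees: "Treatment start date is used as the Analysis Start Date for comparing migalastat and ERT-treated patients". SAP 11.2 uses the diagnosis date as origin for migalastat versus untreated. SAP 13.4 analyses the cardiac, cerebrovascular and renal categories in the same way as the composite. SAP 17.1 records no changes from the protocol.

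**The concern.** A baseline covariate that the protocol specified for the primary endpoint has disappeared, and the section meant to record such changes says there are none.

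Whether this matters depends on the time origin. When the clock starts at diagnosis, the covariate is zero for every patient and nothing is lost. When it starts at first treatment, patients enter the risk set at different distances from diagnosis. For migalastat versus ERT that distance is tied to calendar time, because one drug could not be started before 2016. If time since diagnosis is prognostic given the other covariates, part of its effect would be read as a difference between the two drugs.

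**Working it through.** **Step 1. Compare the lists.**

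| Covariate | Protocol, primary endpoints analysis | SAP 13.1.1 |
|---|---|---|
| Age | yes | yes |
| Previous FACE | yes | yes |
| Time since diagnosis | yes | no |
| Sex, eGFR, LVMi | no | yes |
| Length of treatment | no | yes |

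One protocol covariate is removed and four are added. SAP 17.1 mentions none of this.

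**Step 2. Find the comparisons affected.** Time since diagnosis at the Analysis Start Date is the Analysis Start Date minus the diagnosis date.

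- Migalastat versus untreated (origin at diagnosis, SAP 11.2): the difference is 0 for all patients, so there is no effect.
- Migalastat versus ERT (origin at treatment start, SAP 11.2 and 13.1.1) and its versions in SAP 13.4: the difference varies between patients.

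**Step 3. See how far the groups could differ.** Inputs: follow-up from 01.01.2001 to 31.12.2022 (protocol, Method) and migalastat available from 2016 (protocol, Rationale and background).

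- From 01.01.2001 to 01.01.2016 is 15.0 years. From 01.01.2001 to 31.12.2022 is 22.0 years. A patient diagnosed at the start of follow-up whose first treatment was migalastat would be about 15 to 22 years past diagnosis at treatment start.
- A patient diagnosed in 2006 whose first treatment was migalastat waited at least about 2016 − 2006 = 10 years.
- The documents put no such lower limit on ERT starts. SAP 5.1 and 5.2.1 provide for treatment within 3 months of enrollment, which SAP 11.1 equates with diagnosis.
- A patient diagnosed after 2016 could start migalastat promptly, so a difference is possible but not certain.

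**Step 4. Check whether a listed covariate replaces it.** Age at treatment start equals age at diagnosis plus time since diagnosis. Adjusting for the sum leaves the split between the two parts free. Length of treatment is not defined in the SAP. Measured at the start of a first treatment it is 0 for everyone, and measured as total duration it is a post-baseline quantity. Neither stands in for time since diagnosis.

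**Step 5. Illustrate the size.** The plan has no figure to reproduce: SAP 4 says the sample size was not determined statistically, and the documents give neither the group difference nor the effect per year. Let *h* be the hazard ratio per year since diagnosis and *d* the mean difference in years (migalastat minus ERT), both conditional on the other covariates. The approximate factor on the migalastat/ERT hazard ratio is *h* to the power *d*. All values of *h* and *d* below are assumptions.

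| *h* per year | *d* = 2 | *d* = 5 | *d* = 10 |
|---|---|---|---|
| 1.00 | 1.00 | 1.00 | 1.00 |
| 1.02 | 1.04 | 1.10 | 1.22 |
| 1.05 | 1.10 | 1.28 | 1.63 |

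If ERT patients were the ones diagnosed longer ago, *d* changes sign and the factors invert. The extreme becomes 1/1.63 = 0.61.

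**The case against.** Several points on the other side are sound.

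- **The tested comparison is elsewhere.** A reader might infer that the primary result is biased. SAP 3.2 and 13.1 make that comparison migalastat versus untreated, and with the origin in SAP 11.2 it is untouched. SAP 3.1 gives a different origin (treatment start for treated patients, diagnosis for untreated). That conflict needs reconciling in its own right, and restoring this covariate would not cure it, since the covariate would be zero by construction in the untreated group only.
- **The protocol does not name this hazard ratio.** Its Cox sentence is about baseline characteristics and has no treatment term. It would be too strong to say the protocol planned to adjust the migalastat/ERT contrast. It does set the covariates for the primary endpoint, and the SAP builds its treatment comparisons on that model.
- **The imbalance is possible, not shown.** SAP 3.1 bases the formal analysis on the first treatment received. That would keep patients who moved from ERT to migalastat in the ERT group, although the treatment-naïve subgroup in SAP 12 leaves some doubt. No document says that migalastat starters had been diagnosed longer.
- **The effect per year may be zero or negative.** Diagnosis here means genetic verification, and the centre has long used cascade screening. Given age, an earlier diagnosis may reflect earlier detection rather than more advanced disease. Age, eGFR, LVMi and event history may also absorb part of any difference.
- **Switch periods are not affected.** A reader might extend the point to the analyses after each switch. SAP 3.1 and 13.1.1 make those descriptive, with no covariate list.
- **Dates can be missing.** SAP 6.1 imputes partial therapy dates and sets a completely missing start of a new or switched therapy to 30 days after enrollment, so the covariate will not be exact for everyone. The outcome clock for this comparison depends on the same date, however.
- **Versions differ.** The SAP cites protocol version 2 and the supplied protocol is labelled V1. The list may have changed in between, in which case SAP 17.1 could be accurate.

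These points limit the reach of the concern. They do not remove the omission or supply a substitute covariate.

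**Conclusion.** The point holds for one comparison. On the documents supplied, a covariate specified in the protocol is missing from SAP 13.1.1 and the change is undeclared. The consequence falls on the additional migalastat-versus-ERT Cox analysis and its category versions, where the covariate varies, could differ between groups because of when migalastat became available, and is not replaced by anything in the list.

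The size and direction of bias cannot be known from the documents. The illustrative factor of 1.00 to 1.63, or 0.61 to 1.00 if ERT patients were diagnosed longer ago, rests entirely on assumed effects of 1.00 to 1.05 per year and differences of 2 to 10 years. No bias at all lies within that range, and an effect per year below 1.00 would reverse the direction. A reader might infer that migalastat will look worse than ERT by a predictable amount, but the documents do not support that.

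The change is still worth making: it is cheap, and it removes a possible source of confounding in a comparison that the SAP sets out to report.

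**What to change.** 1. In SAP 13.1.1, add *time from diagnosis to Analysis Start Date (continuous)* to the covariates for migalastat versus ERT, derived under the date rules in SAP 6.1. Apply the same to that comparison in SAP 13.4. The migalastat-versus-untreated model does not need it while the origin is diagnosis.
2. In SAP 17.1, list the covariate differences from the protocol: time since diagnosis removed where it is zero by construction; sex, eGFR, LVMi and length of treatment added. If protocol version 2 already changed the list, say so. If time since diagnosis was left out of migalastat versus ERT on purpose, give the reason there.

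The cost is SAP wording and a variable derived from two dates that the analysis already needs. The downside is one more parameter in a model drawn from about 115 patients, and some values that rest on imputed therapy start dates.
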